### Events NOT Meeting the AE Definition

- Any clinically significant abnormal laboratory findings or other abnormal safety assessments which are associated with the underlying disease, unless judged by the Investigator to be more severe than expected for the participant's condition.
- The disease/disorder being studied or expected progression, signs, or symptoms of the disease/disorder being studied, unless more severe than expected for the study participant's condition.
- Medical or surgical procedure (eg, endoscopy, appendectomy): the condition that leads to the procedure is the AE.
- Situations in which an untoward medical occurrence did not occur (social and/or convenience admission to a hospital).
- Anticipated day-to-day fluctuations of pre-existing disease(s) or condition(s) present or detected at the start of the study that do not worsen.

### 10.3.2 Definition of SAE

If an event is not an AE per definition above, then it cannot be an SAE even if serious conditions are met (eg, hospitalization for signs/symptoms of the disease under study, death due to progression of disease).

#### An SAE is defined as any untoward medical occurrence that, at any dose:

##### a. Results in death

##### b. Is life-threatening

The term 'life-threatening' in the definition of 'serious' refers to an event in which the participant was at risk of death at the time of the event. It does not refer to an event, which hypothetically might have caused death, if it were more severe.

##### c. Requires inpatient hospitalization or prolongation of existing hospitalization

In general, hospitalization signifies that the participant has been detained (usually involving at least an overnight stay) at the hospital or emergency ward for observation and/or treatment that would not have been appropriate in the physician's office or outpatient setting. Complications that occur during hospitalization are AEs. If a complication prolongs hospitalization or fulfills any other serious criteria, the event is serious. When in doubt as to whether "hospitalization" occurred or was necessary, the AE should be considered serious.

Hospitalization for elective treatment of a pre-existing condition that did not worsen from baseline is not considered an AE.

**d. Results in persistent disability/incapacity**

- The term disability means a substantial disruption of a person's ability to conduct normal life functions.
- This definition is not intended to include experiences of relatively minor medical significance such as uncomplicated headache, nausea, vomiting, diarrhea, influenza, and accidental trauma (eg, sprained ankle) which may interfere with or prevent everyday life functions but do not constitute a substantial disruption.

**e. Is a congenital anomaly/birth defect**

**f. Important medical events:**

- Medical or scientific judgment should be exercised in deciding whether SAE reporting is appropriate in other situations such as important medical events that may not be immediately life-threatening or result in death or hospitalization but may jeopardize the participant or may require medical or surgical intervention to prevent one of the other outcomes listed in the above definition. These events should usually be considered serious.

Examples of such events include, but are not limited to, potential Hy's Law, invasive or malignant cancers, intensive treatment in an emergency room or at home for allergic bronchospasm, blood dyscrasias or convulsions that do not result in hospitalization, or development of drug dependency or drug abuse.

### 10.3.3 Recording and follow up of AE and/or SAE

#### AE and SAE Recording

- When an AE/SAE occurs, it is the responsibility of the Investigator to review all documentation (eg, hospital progress notes, laboratory reports, and diagnostics reports) related to the event.
- The Investigator will then record all relevant AE/SAE information in the eCRF.
- It is **not** acceptable for the Investigator to send photocopies of the participant's medical records to UCB in lieu of completion of the UCB AE/SAE eCRF page.
- There may be instances when copies of medical records for certain cases are requested by UCB. In this case, all participant identifiers, with the exception of the participant number, will be redacted on the copies of the medical records before submission to UCB.
- The Investigator will attempt to establish a diagnosis of the event based on signs, symptoms, and/or other clinical information. Whenever possible, the diagnosis (not the individual signs/symptoms) will be documented as the AE/SAE.

#### Assessment of Intensity

The Investigator will make an assessment of intensity for each AE and SAE reported during the study and assign it to one of the following categories:

- **Mild:** An event that is easily tolerated by the participant, causing minimal discomfort and not interfering with everyday activities.
- **Moderate:** An event that causes sufficient discomfort and interferes with normal everyday activities.
- **Severe:** An event that prevents normal everyday activities. An AE that is assessed as severe should not be confused with a SAE. Severe is a category utilized for rating the intensity of an event; and both AEs and SAEs can be assessed as severe.
- An event is defined as 'serious' when it meets at least one of the predefined outcomes as described in the definition of an SAE, NOT when it is rated as severe (eg, a severe AE may be either serious or not serious, depending on whether these criteria are also met).

The National Cancer Institute Common Terminology Criteria for Adverse Events should be used as a supportive standardization instrument to evaluate AEs and SAEs, but the final intensity grading by the Investigator must be mild, moderate, or severe.

### Assessment of Causality

- The Investigator is obligated to assess the relationship between study medication and each occurrence of each AE/SAE.
- A "reasonable possibility" of a relationship conveys that there are facts, evidence, and/or arguments to suggest a causal relationship, rather than a relationship cannot be ruled out.
- The Investigator will use clinical judgment to determine the relationship.
- Alternative causes, such as underlying disease(s), concomitant therapy, and other risk factors, as well as the temporal relationship of the event to study medication administration, will be considered and investigated.
- The Investigator will also consult the Investigator's Brochure (IB) and/or Product Information, for marketed products, in his/her assessment.
- For each AE/SAE, the Investigator **must** document in the medical notes that he/she has reviewed the AE/SAE and has provided an assessment of causality.
- There may be situations in which an SAE has occurred and the Investigator has minimal information to include in the initial report to UCB. However, **it is very important that the Investigator always make an assessment of causality for every event before the initial transmission of the SAE data to UCB.**
- The Investigator may change his/her opinion of causality in light of follow up information and send a SAE follow up report with the updated causality assessment.
- The causality assessment is one of the criteria used when determining regulatory reporting requirements.

### Follow-up of AEs and SAEs

- The Investigator is obligated to perform or arrange for the conduct of supplemental measurements and/or evaluations as medically indicated or as requested by UCB to elucidate the nature and/or causality of the AE or SAE as fully as possible. This may include additional laboratory tests or investigations, histopathological examinations, or consultation with other health care professionals.
- An AE should be followed until it has resolved, has a stable sequelae, the Investigator determines that it is no longer clinically significant, or the participant is lost to follow up. This follow up requirement applies to AEs, SAEs, and AEs of special interest.
- If a participant dies during participation in the study or during a recognized Follow-Up Period, the Investigator will provide UCB with a copy of any post-mortem findings including histopathology.
- New or updated information will be recorded in the originally completed eCRF.
- The Investigator will submit any updated SAE data to UCB within 24 hours of receipt of the information.

### Reporting of SAEs

#### SAE Reporting to UCB via an Electronic Data Collection Tool

- The primary mechanism for reporting an SAE to UCB will be the electronic data collection tool.
- If the electronic system is unavailable for more than 24 hours, then the site will use the paper SAE data collection tool (see next section).
- The site will enter the SAE data into the electronic system as soon as it becomes available.
- After the study is completed at a given site, the electronic data collection tool will be taken off-line to prevent the entry of new data or changes to existing data.
- If a site receives a report of a new SAE from a study participant or receives updated data on a previously reported SAE after the electronic data collection tool has been taken off-line, then the site can report this information on a paper SAE form (see next section) or to the UCB Study Physician by telephone.
- Contacts for SAE reporting can be found in [SERIOUS ADVERSE EVENT REPORTING](#).

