### **7.1.2 Criteria for study hold due to adverse events**

In recognition of the advanced status of the development program for PSL, the following study hold/stopping rules will apply to this study.

In the event that either or both of the following criteria are met, a safety review will be immediately initiated:

- The occurrence of a serious adverse reaction (SAR) (ie, an SAE considered at least possibly related to the study medication) in 2 study participants, where those SARs occur in the same body system.
- The occurrence of a severe nonserious adverse reaction (ie, severe nonserious AEs considered at least possibly related to the study medication) in 3 study participants, where those severe ARs
  - occur in the same body system, and
  - lead to the withdrawal of the affected participant

The safety review will be conducted by an internal, study-specific Safety Monitoring Committee comprised of the Investigator and appropriate members of the UCB Study Team (such as Study Physician, Safety Physician, Clinical Project Manager, Clinical Pharmacologist), as quickly as possible, to review the available data and determine whether it is appropriate to continue dosing at the next scheduled dosing point. This will take the form of a risk/benefit evaluation from the perspective of the individual study participants. In making this evaluation, account will be taken of the potential risks of sudden discontinuation of study medication, particularly in participants who may be taking higher dose levels, and whether or not a tapering period, and its duration/speed, should be undertaken.

The Safety Monitoring Committee will also decide whether it is appropriate to continue the study with or without dose adaptations, additional safety assessments, or other changes in design. If such changes are deemed necessary to protect the wellbeing of participants, further dosing in the study will be suspended while a substantial amendment is submitted to the Country(ies) Health Authority and Research Ethics Committee(s) and the study will not restart until that amendment has been approved.

If the Safety Monitoring Committee cannot be convened before the next scheduled dosing point, the Investigator will make an independent evaluation as to whether it is appropriate to continue dosing pending the review.

Detailed procedures for reporting SAEs and other safety events which may meet study hold/stopping criteria are provided in Appendix 3 (see Section 10.3).

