##### **8.5.1 Time period and frequency for collecting AE and SAE information**

All AEs and SAEs will be collected from the signing of the ICF and at the time points specified in the Schedule of Activities ([Table 1-3](#)).

Medical occurrences that begin before the start of study medication, but after obtaining informed consent will be recorded on the Medical History/Current Medical Conditions section of the eCRF, not the AE section.

All SAEs will be recorded and reported to the Sponsor or designee within 24h, as indicated in Appendix 3 (Section [10.3](#)). The Investigator will submit any updated SAE data to the Sponsor within 24h of it being available.

The Investigator is specifically requested to collect and report to UCB (or its representative) any SAEs (even if the Investigator is certain that they are in no way associated with the study medication), up to 30 days from the end of the study for each participant, and to also inform participants of the need to inform the Investigator of any SAE within this period. Serious AEs that the Investigator thinks may be associated with the study medication must be reported to UCB regardless of the time between the event and the end of the study.

The method of recording, evaluating, and assessing causality of AE and SAE and the procedures for completing and transmitting SAE reports are provided in Appendix 3 (Section [10.3](#)).

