### SAE Reporting to UCB via Paper CRF

- Facsimile transmission of the SAE paper CRF is the preferred method to transmit this information to the UCB Study Physician.
- In rare circumstances and in the absence of facsimile equipment, notification by telephone is acceptable with a copy of the SAE data collection tool sent by overnight mail or courier service.
- Initial notification via telephone does not replace the need for the Investigator to complete and sign the SAE CRF pages within the designated reporting time frames.
- Contacts for SAE reporting can be found in [SERIOUS ADVERSE EVENT REPORTING](#).

This document cannot be used to support any marketing authorization application and any extensions or variations thereof.

REDACTED COPY

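### The written switch to the paper SAE form comes only after an outage of more than 24 hours, which does not fit inside the protocol's own 24-hour SAE reporting limit

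*Protocol*

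**What the plan says.** Protocol Section 8.5.1 sets the limit and says where the method is described: "All SAEs will be recorded and reported to the Sponsor or designee within 24h, as indicated in Appendix 3". It makes no exception for a system outage. Updated SAE data carry the same limit, in Section 8.5.1 ("The Investigator will submit any updated SAE data to the Sponsor within 24h of it being available") and again in Appendix 3 under follow-up of AEs and SAEs ("The Investigator will submit any updated SAE data to UCB within 24 hours of receipt of the information").

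Appendix 3, Section 10.3.3, gives the method. "The primary mechanism for reporting an SAE to UCB will be the electronic data collection tool". The fallback rule follows: "If the electronic system is unavailable for more than 24 hours, then the site will use the paper SAE data collection tool". The data are then entered electronically when the system returns.

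The next part of Section 10.3.3 covers the paper form. Facsimile is the preferred way to send it. A second way is limited: "In rare circumstances and in the absence of facsimile equipment, notification by telephone is acceptable". Telephone notice does not release the investigator from completing the written pages on time.

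A separate rule in Section 10.3.3 allows paper or telephone reporting after the electronic tool has been closed at the end of the study at a site. That rule has no waiting time.

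**The concern.** A fallback exists so that a deadline can be met when the main route fails. Here the wait before the fallback opens is longer than the deadline itself. Section 8.5.1 sends the site to Appendix 3 for the method, and a site that follows Appendix 3 to the letter can be waiting for the paper route to open when its 24 hours run out.

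What is at stake is the timeliness of formal SAE notification to the Sponsor. Section 8.5.4 treats prompt notification as necessary for the Sponsor's legal and ethical duties. No endpoint, analysis set, sample size or PK comparison is touched.

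**Working it through.** No statistical figure is involved. The check compares two time limits.

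**Inputs**
- Reporting limit: 24 h (Protocol 8.5.1). The sentence does not say when the clock starts for a first report. I assume it starts when the site becomes aware of the SAE, t = 0.
- Paper trigger: an outage of more than 24 h (Protocol 10.3.3).
- Start of the outage relative to awareness: *a* hours, negative if the system was already down.

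**Formulas**
- Deadline: t = 24 h.
- Paper route opens: later than t = *a* + 24 h.
- Opening time minus deadline: more than (*a* + 24) − 24 = *a* hours. The written fallback is therefore late whenever *a* is zero or positive.

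**Results, for an outage that lasts long enough to meet the trigger**

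| Outage starts | Paper route opens | Against the 24 h limit |
|---|---|---|
| 24 h or more before awareness (*a* ≤ −24) | at once or almost at once | in time |
| 6 h before awareness (*a* = −6) | just after 18 h | in time, just under 6 h left |
| at awareness (*a* = 0) | after 24 h | limit has passed |
| 6 h after awareness, SAE not yet entered (*a* = +6) | after 30 h | more than 6 h late |
| just under 24 h after awareness | after about 48 h | about 24 h late |

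The last row should be read with care. Almost 24 of its 48 hours pass with a working system before the outage begins, so most of the delay up to the deadline does not come from the fallback rule.

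**Shorter outages.** An outage can block the electronic route past the deadline without ever meeting the trigger. If it runs from hour 20 to hour 40 it lasts 40 − 20 = 20 h, less than the 24 h needed, yet it covers the deadline at hour 24.

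**Do the other reporting rules open the paper route sooner?** Facsimile and telephone are described as ways to transmit the paper report, and neither carries an earlier trigger. The allowance without a wait applies only after the tool has been closed at the end of the study at a site. So no rule in the reviewed text tells the site to move to paper within the first 24 hours of an outage.

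**The case against.** Four points can be made on the other side.

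1. **Earlier paper use is not forbidden.** Section 10.3.3 says when the site will move to paper, not that it may not do so sooner. The limit in Section 8.5.1 is unconditional, and the paper pages are themselves due within the reporting time. A careful site reading these together would send paper in time. This stands, and it is a main reason why the point is minor. It does not remove the conflict, because the only written instruction for an outage carries the wait.

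2. **Another route may exist.** Section 10.3.3 refers sites to the SAE reporting contact page at the front of the protocol. That page is not in the reviewed text, so it cannot be said that no other route exists. This stands.

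3. **The breach is conditional.** It needs an outage that starts at or after awareness and covers the rest of the window. The documents do not say how often outages occur. This stands.

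4. **No safety decision is shown to depend on the sentence.** A reader might infer that a late SAE report delays the study hold, so that participants receive further doses that could be counted. The inference is tempting because Section 7.1.2 says "In the event that either or both of the following criteria are met, a safety review will be immediately initiated" and refers to Appendix 3 for reporting. The documents do not support it:
   - The hold criteria are met when the reactions occur, not when an electronic report arrives.
   - The study has one site (SAP 3.7 and 4.6) and participants stay in the clinic until Day 18. The investigator judges causality for every SAE and sits on the Safety Monitoring Committee.
   - If the committee cannot meet before the next dose, Section 7.1.2 has the investigator decide independently about dosing in the meantime.
   - The opening of Section 8 asks for urgent safety concerns to be raised with the Study Physician straight away, without reference to the electronic tool.
   - A dose count would also require the event to fall in the twice-daily phase. No drug is given on Days 2 to 7 or 13 to 17.

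**Conclusion.** Two written rules conflict: a 24 h limit for reporting an SAE, and a fallback that opens only after more than 24 h of outage. When the outage starts at or after awareness and covers the rest of the reporting window, the fallback opens too late by more than the interval between awareness and the start of the outage. When the outage began well before awareness, there is no breach. Updated SAE data meet the same problem.

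The demonstrated consequence is late formal SAE notification to the Sponsor and nothing beyond that. The conclusion assumes that the clock starts at awareness and that the site follows Section 10.3.3 literally. It is also subject to what the SAE contact page says. Severity: minor.

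**What to change.** Reconcile Section 8.5.1 with the electronic and paper parts of Section 10.3.3. In the fallback sentence, delete the condition that the outage has lasted more than 24 hours. State instead that, if the electronic system is unavailable, the site uses the paper SAE form by the existing routes so that the SAE is reported within 24 h of awareness, and enters the data electronically once the system is back. Naming awareness as the start of the clock in Section 8.5.1 would remove the assumption made here. Check the SAE contact page for consistency at the same time.

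The cost is small: one sentence in Appendix 3, a few words in Section 8.5.1, and the site's SAE instructions. The paper form and the facsimile route already exist. The downside is some duplicate paper and electronic entry during short outages.

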### SAE Reporting to UCB via Paper CRF

- Facsimile transmission of the SAE paper CRF is the preferred method to transmit this information to the UCB Study Physician.
- In rare circumstances and in the absence of facsimile equipment, notification by telephone is acceptable with a copy of the SAE data collection tool sent by overnight mail or courier service.
- Initial notification via telephone does not replace the need for the Investigator to complete and sign the SAE CRF pages within the designated reporting time frames.
- Contacts for SAE reporting can be found in [SERIOUS ADVERSE EVENT REPORTING](#).

This document cannot be used to support any marketing authorization application and any extensions or variations thereof.

REDACTED COPY

## **10.4 Appendix 4: Contraceptive guidance and collection of pregnancy information**

### **10.4.1 Definitions**

#### **10.4.1.1 Woman of childbearing potential**

A woman is considered fertile following menarche and until becoming post-menopausal unless permanently sterile (see below).

Women in the following categories **are not considered WOCBP**:

1. Premenarchal
2. Premenopausal female with 1 of the following:
  - Documented hysterectomy
  - Documented bilateral salpingectomy
  - Documented bilateral oophorectomy

Note: Documentation can come from the site personnel's review of the participant's medical records, medical examination, or medical history interview.

3. Postmenopausal female
  - A postmenopausal state is defined as no menses for 12 months without an alternative medical cause. A high follicle stimulating hormone (FSH) level in the postmenopausal range may be used to confirm a postmenopausal state in women not using hormonal contraception or hormonal replacement therapy (HRT). However, in the absence of 12 months of amenorrhea, a single FSH measurement is insufficient.
  - Females on HRT and whose menopausal status is in doubt will be required to use one of the non-estrogen hormonal highly effective contraception methods if they wish to continue their HRT during the study. Otherwise, they must discontinue HRT to allow confirmation of postmenopausal status before study enrollment.

